3.1. Study Design

This is a two-phase, 3 year, randomized, single-blind, parallel group, contact controlled pilot trial of OXT augmentation of CBI groups in youth with ASD. Phase 1 (n=10) is an initial development trial to refine manuals, procedures, and outcome evaluations. Phase 2 (n=70) will evaluate feasibility, safety, and preliminary efficacy of ION-ASD relative to the contact control (i.e. social play group). All participants are expected to be outpatients and will participate in a 12-session group therapy, with a follow-up study visit at 24 weeks. Evaluations will be conducted at four time points: Screening, Baseline, Endpoint (week 12), and Follow-up (1-month & 3-months post-treatment).

Each phase will randomly assign in a 1:1 ratio to either ION-ASD or control in blocks of 10. Efficacy outcomes will be evaluated by both caregiver report and blinded independent evaluators (IE); safety assessments will be conducted by unblinded treating medical clinicians (Medical TC). Caregivers and participants will be instructed to conceal group assignment from IEs. IEs, participants, and caregivers will also be instructed on reporting strategies should group assignment be revealed. Corrective action plans in these scenarios will be employed if necessary and include changing IE raters and flagging data. IEs will be asked to “guess” patient conditions at the end of the trial to evaluate integrity of the blind.

Medical TCs will monitor side-effects using weekly ratings with the participant and caregiver. Clinical IEs will evaluate global functioning and social communication skills. Neurocognitive IEs will conduct blinded neurocognitive assessments (see Appendix A: Time & Events Schedule).

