3.7. Participant Withdrawal Criteria

Participants will be withdrawn from the study treatment if they meet one or more of the following criteria:

1. CGI-I ≥ 6 on two consecutive visits
2. If they become pregnant during the study
3. If they have blood pressure above 99th percentile for age, gender, and height on two consecutive visits (*range in accordance with the Fourth Report on the Diagnosis, Evaluation, and Treatment of High Blood Pressure in Children and Adolescents (U.S. Department of Health and Human Services)⁵³)
4. If they have blood pressure above the 99th percentile for age, gender, and height on two consecutive visits
5. If they experience an adverse event that is deemed by the Medical Independent Evaluator (IE) to be an unacceptable safety risk
 - o If the Study clinician feels it is in the participant's best interest to discontinue the study treatment

4. Study Assessments

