4.3. Safety Assessments

Adverse events will be systematically reviewed by study clinician and each study will have a back-up physician to assess safety. The study clinician will also do a general inquiry about health, other medications, and visits to medical care providers since the last visit. The following safety measures will be completed either in-person or may take place virtually via a HIPAA compliant platform (i.e. Zoom) if needed to reduce the amount of in person interaction between study team and participant.

- *Clinical Global Impressions – Improvement Scale – Global (CGI-I)*. The CGI-I employs a seven point (1 = very much improved to 7 = very much worse) to determine the patient's improvement in response to treatment. The CGI-I has been successfully used as an outcome measure in previous psychopharmacology trials including the RUPP trial of risperidone in children with ASD, and the STAART funded citalopram trial. The rating convention for assigning CGI scores is to use all available data including direct observation, scales, and patient report to inform clinical judgment. CGI-I, Global will be used to evaluate safety, with the requirement that individuals scoring CGI of 6 or greater for 2 or more weeks be discontinued from the study and provided with appropriate referrals.
- *Adverse event rating form*
This is a semi-structured interview that has been modified to assess OXT specific side effects for a recently completed pediatric trial of sustained oxytocin treatment in ASD ⁵². It contains a general inquiry, drug-specific queries, as well as several questions about daily activities (e.g., sleep, appetite, energy level, bowel and bladder function). This instrument has been widely used in other autism related clinical trials. In addition to these measures, vital signs (heart rate, blood pressure) will be measured biweekly at the following visits: screening, baseline/week 1, week 3, week 5, week 7, week 9, week 11, week 12, week 16, and week 24 (or another biweekly schedule depending on start days/dates) Standardized procedures will be used for all physical measurements. We will attempt to do vital signs following a 4 minute period of rest, with the participant seated. Height and Weight will be taken at screening, baseline, Week 12, and Week 24 with all outer wear and shoes removed at every visit.

5. Study Treatment

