Participants entering the study will undergo the baseline assessments, which are anticipated to take approximately 6-10 hours to complete no more than 21 days from the last screening visit. The visit can be split into as many as three visits if this is better for the participant. The following measures will be completed: the CGI-S (Global and Social), AE rating form, the RMET, the CASI-5, the RBS-R, the SRS, the BASC-3, the PDDBI-SV, the Griffith Empathy Scale, the Children's Communication Checklist, the Caregiver Strain, the DANVA2, the TAT, and the Test, GEMEP emotion recognition test, and sensor-based social-communication monitoring tests..

Vineland Scales of Adaptive Functioning (3rd edition): The VABS-3 is a survey administered to a parent or caregiver is organized around four Behavior Domains: Communication, Daily Living Skills, Socialization, and Motor Skills. The VABS-3 will take the parent/caregiver/LAR approximately 20-60 (average 30) minutes to complete, depending on the subject's age and level of functioning.

Weekly Visits (1-11)

Interventions are delivered in 12-session modules occurring on a weekly basis. Groups will commence when all participants in a cycle have completed baseline evaluations and within 21 days of participant's last baseline visit. Participants will receive group treatment conditions as described in Section 5.1 (Treatment Conditions). Participants randomized to ION will also be prescribed 24 IU (3 puffs/nostril) of intranasal oxytocin 4 times/week to be administered by the parent 30-minutes prior to homework practice (3 x/week) and 30 minutes prior to each weekly group session.

Safety ratings during group: Weeks 1, 3, 5, 7, 9, 11 (or biweekly schedule depending on group start day/date)

Vital signs, temperature, and AE ratings will be completed in 6/12 sessions by a licensed physician on participants in all groups. In addition, the CGI-I (Global and Social) will be completed by the Study clinician. At

Confidential

Rush University Medical Center

Week 6, the CY-BOCS, the CASI-5, the RBS-R, the PDDBI-SV, the Griffith Empathy Scale, the Children's Communication Checklist, the Caregiver Strain and the ABC will be completed. In addition, a two week supply of study drug will be dispensed at weeks 1, 3, 5, 7, 9, 11. Unplanned visits will be permitted if there are any concerns about AEs. Safety visits are expected to take 15-20 minutes.

Week 6 (Midpoint)

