- Unanticipated fatal or life threatening adverse events (7 days)
- Unanticipated non-fatal/non-life threatening events (14 days)

Other reportable events

Other reportable will be reported during the annual review. Other reportable events with shorter reporting intervals include pregnancy of subject or the subject's sexual partner and serious intentional self-harm or serious suicidal ideation.

- In case of a pregnancy, investigators will follow the pregnancy until completing (either termination or birth). The baby will be followed until s/he is 1 month old to assess and record any medical complications. The initial report will be sent to the IRB within 7 days of the study team's awareness.
- In case of serious intentional self-harm or serious suicidal ideation, the physician/clinician should take necessary steps to ensure the safety of the participant including involuntary hospitalization (if needed). This should be reported (on the appropriate source document) to the IRB within 7 days of the study team's awareness.

Stopping procedures.

Subjects may be withdrawn from the study for any of the following reasons:

- At the participant or guardian's request
- If moderate or severe AEs occur that cannot be addressed by the PI, Study clinician or medical monitor
- If a subject is worsening clinically (i.e. have CGI-I = 6 (much worse) or 7 (much worse)) and there has been a return visit/call within 1-2 weeks to revisit/re-evaluate the CGI-I. If subject remains at a CGI-I = 6 or 7, the case can be discussed with the medical monitor to get approval for the participant to continue
- Study noncompliance
- Study physician/clinician discretion

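### For a child whose CGI-I stays at 6 or 7, the protocol gives incompatible rules: mandatory treatment withdrawal, mandatory study discontinuation, or optional withdrawal with possible continuation

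*Protocol*

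**What the plan says.** Four places in the protocol attach a consequence to a persistently poor CGI-I.

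- **Section 3.7 (Participant Withdrawal Criteria)** opens with "Participants will be withdrawn from the study treatment if they meet one or more of the following criteria" and lists "CGI-I ≥ 6 on two consecutive visits" first. It states no exception to that criterion.
- **Section 4.2 (Efficacy Assessments, CGI-I)** and **Section 4.3 (Safety Assessments)** carry the same requirement, that "individuals scoring CGI of 6 or greater for 2 or more weeks be discontinued from the study", with referral. Neither states an exception.
- **Section 8.5 (Stopping procedures)** opens with "Subjects may be withdrawn from the study for any of the following reasons". For a CGI-I of 6 or 7 it adds the condition that "there has been a return visit/call within 1-2 weeks to revisit/re-evaluate the CGI-I". If the score is still 6 or 7, "the case can be discussed with the medical monitor to get approval for the participant to continue".

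Two other places matter. Section 5.2 and Appendix A put the study clinician's CGI-I at weeks 1, 3, 5, 7, 9 and 11, and Appendix A continues it at weeks 12, 16 and 24. The Termination Visit text in Section 5.2 asks withdrawing participants to complete the endpoint procedures at their last visit, so that an intent-to-treat analysis is possible. The SAP does not mention the rule.

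**The concern.** This is a stopping rule for individual children aged 8-11, some of them on an investigational drug. Site staff who read only Section 8.5 could keep a worsening child in the trial with the medical monitor's agreement. They would then be in breach of Sections 3.7, 4.2 and 4.3. Staff who read only Section 3.7 would stop treatment and could keep the child in follow-up, in breach of 4.2 and 4.3.

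There is also a statistical consequence. Whether exit is from treatment or from the study bears on which later outcomes are collected. The children concerned are by definition those doing worst, so any gaps in their data would be related to outcome, and the gaps would depend on which section the staff happened to follow.

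**Working it through.** There is no figure in the plan to reproduce, so the check sets the rules side by side and runs one case through them.

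| | 3.7 | 4.2 and 4.3 | 8.5 |
|---|---|---|---|
| Trigger | CGI-I of 6 or more at two consecutive visits | CGI of 6 or more for at least 2 weeks | CGI-I of 6 or 7, rechecked by visit or call within 1-2 weeks |
| Obligation | Mandatory | Mandatory | Discretionary |
| Ends | Study treatment | Study participation | Study participation, if exercised |
| Way to continue | None stated | None stated | Medical-monitor approval |

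**Do the triggers conflict?** Only a little. With ratings at weeks 1, 3, 5, 7, 9 and 11, two consecutive visits are nominally (5 − 3) × 7 = 14 days apart, which equals the 2 weeks in 4.2 and 4.3. Three departures remain:

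- The ±2-day allowance for a missed group meeting could bring a pair to 14 − 2 = 12 days.
- Weeks 11 and 12 are 7 days apart, but treatment is then ending.
- A recheck at one week under 8.5 falls before the other two triggers are met.

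**Do the consequences conflict?** Take a child rated 6 at weeks 3 and 5. The two visits are consecutive, 14 days have passed, and the score has been rechecked within 2 weeks and is still 6. All three triggers are met:

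- Under 3.7, treatment must stop.
- Under 4.2 and 4.3, study participation must end.
- Under 8.5, withdrawal is optional and the child can continue with approval.

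**Can the sections be read together?** I tried three readings.

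1. Section 8.5 means off treatment but still in the study. This fits 3.7 but contradicts the required study discontinuation in 4.2 and 4.3.
2. Section 8.5 is an exception to the others. Nothing says so: 3.7, 4.2 and 4.3 are unconditional on this point and do not mention the medical monitor.
3. Section 3.7 is a minimum to which 4.2 and 4.3 add. That reconciles those three, but the optional wording and the route to continue in 8.5 still contradict them.

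**What happens to the data?** The Statistical analysis section of the protocol admits participants with at least two of four time points (baseline, week 12, 1 month, 3 months). For the same child:

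- If only treatment stops, assessments at weeks 12, 16 and 24 remain possible, although the protocol does not expressly say they continue.
- If study participation ends, the child has baseline and an endpoint battery at about week 5, and nothing on schedule afterwards. Neither document says whether that early battery is analysed as week 12. If it is, the child has 2 of 4 time points and enters the model. If not, the child has 1 of 4 and does not.
- If continuation is approved, the full schedule applies.

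**The case against.** The best defence is that the differences are mostly loose wording. The protocol may use withdrawal and discontinuation interchangeably, the first two triggers coincide on the actual schedule, and the 8.5 recheck can be read as the step that establishes persistence. Section 8.5 also sends continuation through medical review, so a worsening child is not left unmanaged, and 3.7 separately lets the clinician stop treatment. Most of this stands as far as the triggers go. It does not remove the clash between a mandatory exit and an optional one, which no cross-reference settles.

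Several stronger readings are tempting and should not be made.

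- **That the time to action doubles because visits are weekly in one section and biweekly in another.** Section 3.1 says "Medical TCs will monitor side-effects using weekly ratings with the participant and caregiver", and Section 5.2 says "AE ratings will be completed in 6/12 sessions by a licensed physician". Both statements concern adverse effects. Where the safety CGI-I schedule is given, it is biweekly during treatment. The two sections may disagree on how often adverse events are rated, but that is a separate matter.
- **That study discontinuation loses all outcome data.** The Termination Visit text asks for the endpoint procedures at the last visit and for the week 12 blood work when drug is stopped early. One assessment after worsening is therefore planned, and what may be lost is the on-schedule follow-up.
- **That a single rating of 6 triggers action.** Every rule needs a score that persists or is rechecked.
- **That the primary estimate is shown to be biased.** The documents give no count of such children, and no effect on the estimate can be calculated.

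**Conclusion.** The contradiction is real and needs to be fixed. For a child whose CGI-I remains at 6 or 7, following Section 8.5 can breach Sections 3.7, 4.2 and 4.3, and following 3.7 alone can breach 4.2 and 4.3. The main conflict is mandatory against discretionary exit, and treatment against study withdrawal; the difference in triggers is minor.

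The case for fixing it rests on the inconsistency in a safety rule, not on frequency or on demonstrated bias. The effect on data is secondary and conditional. It assumes that withdrawal from treatment alone would allow scheduled assessments to continue, which the protocol implies but does not state, and it is partly limited by the endpoint procedures requested before withdrawal. This review takes no position on which clinical rule is right.

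**What to change.** Reconcile Sections 3.7, 4.2, 4.3 and 8.5 into one rule, stated once, with the other sections referring to it. The rule should give:

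- the trigger, in one unit that fits the biweekly CGI-I schedule;
- whether it is mandatory;
- whether medical-monitor approval can override it;
- whether it ends study treatment or study participation.

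Then align the Termination Visit text in Section 5.2 with it: say which of the week 12, 16 and 24 assessments are still sought, and to which time point an early endpoint assessment is assigned. One matching sentence in the SAP would cover the last item. The clinical content is for the sponsor and the safety board to decide.

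The cost is a wording amendment, with the IRB submission and safety-board review that the protocol already requires for amendments. Reconciling the wording does not of itself change the sample size or the analysis model.

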8.6. Safety Oversight

Data Safety Monitoring Committee (DSMC)

A local DSMC was created to ensure that the safety of study participants is protected and that the scientific goals of the study are being met. To support those purposes, the DSMB will: 1) review any proposed amendments to the study protocol, 2) perform expedited monitoring of all SAEs, 3) perform on-going monitoring of drop-outs and non-serious adverse events; 4) determine whether study procedures should be changed or the study should be halted for reasons related to the safety of study subjects, and 5) perform periodic review of the completeness and validity of data to be used for analysis of safety & efficacy. The DSMB will also ensure subject privacy and research data confidentiality. The DSMB will consist of three members with experience in conducting clinical trials for childhood psychiatric and neurodevelopmental disorders, expertise in biostatistics, and a thorough knowledge of clinical trial ethics and human protection issues. The Rush-based DSMB is be led by [name] a child and adolescent psychiatrist and will also include [name], a pediatric neurologist with extensive clinical trial experience in neurodevelopmental disabilities and [name], lead biostatistician in the Department of Nursing at Rush.

Cardiac Monitoring Plan

Based on the patient's age, gender, and height percentile, we have adapted blood pressure parameters where blood pressures above or below the set threshold will prompt the PI to consider doing an EKG. These parameters were derived from the National High Blood Pressure Education Program Working Group on High Blood Pressure in Children and Adolescents⁷³. We have likewise adapted parameters from Pediatric cardiology for practitioners⁷⁴ and Normal ECG standards for infants and children⁷⁵ to establish heart rate guidelines where patients whose heart rate is above or below these thresholds will be considered for an EKG at every visit. Finally, we will incorporate clinical signs and symptoms of cardiac risk into our assessment with the vital sign measurement and specifically query for the presence of syncope, dizziness, palpitations, shortness of breath,

and bradycardia or tachycardia. The clinical parameters will be incorporated into the AE form. The specific parameters for heart rate, blood pressure are located in Appendix A. We believe, given the low cardiac risk of oxytocin, that careful monitoring of vital signs and clinical signs and symptoms at screening/baseline, biweekly during group, week 16, and week 24. Data Management & Statistical considerations

8.7. Site Monitoring and Data Management

The PI and Project Manager will monitor the study to ensure human subject protection, study procedures, study intervention administration, and data collection processes are maintained and meet regulatory guidelines. The Project Manager will monitor the database, with the PI and statistical consultant, in order to assess quality and control issues. The Project Manager will also review regulatory documents for completeness and accuracy (e.g. delegation log, 1572s, general and IRB correspondence, lab values). The Project Manager will also review case report forms (CRFs) to ensure data are complete and accurate, issue queries for data management team, and ensure queries are resolved. The database will be entered and then checked with CRFs by separate members of the data entry team. Data will also be collected on videos, eye-tracking software from wearable camera glasses (e.g. Google glasses), and 3-D cameras to detect motion. These data are kept on secure, local Rush servers and shared via encrypted, HIPAA compliant websites.

8.8. Statistical analysis

Specific Aim 1 & Exploratory Aim 1: Safety and tolerability will be analyzed by analyzing for group differences on total scores and domains of the AE form and satisfaction surveys respectively. Efficacy analysis will be follow analytic procedures used to derive social behavior and social cognition composites for the Seaver-NETT RCT¹⁶. First, a principal components analysis with varimax (orthogonal) rotation will be conducted on subscales of the primary social behavior measures - Griffith Empathy Scale and CCC-2; and raw total scores on primary social cognition outcomes – RMET and DANVA2. The PCA is used to develop composite scores in a field with no viable outcomes for higher-order core social impairments as well as to minimize floor and ceiling artifacts, effects of variability in response, and other sources of measurement error. Variables with high factor loadings for subscales will be entered into composite score development for the social cognition and social behavior composites. Missing, invalid, and/or incomplete data (i.e. more than 30% items missing when not pre-defined by scale) will be excluded from the factor analysis.

A linear mixed model analysis will be conducted on all participants with at least two of four available time points (Wk 0, Wk 12, 1-mon, 3-mo). Composite scores of co-primary outcomes social behavior and social cognition will be used as the response variable; treatment condition, time, and condition * time interactions will be covariates. Verbal IQ will also be entered into the model in exploratory moderator analyses. We will estimate effect sizes (Cohen's d) and confidence intervals (95%) acknowledging the likelihood that analyses may not permit definitive conclusions given the likely size of the confidence intervals.

